6.3.1.4 Eligibility criteria for individuals performing the interventions

All surgeons should be proficient in the use of CXL linking treatment and will have performed at least 20 procedures.

6.3.1.5 Co-enrolment guidance

The Principal Investigator or Co-Investigator(s) at trial sites will be responsible for ascertaining whether the patient is currently taking part in a clinical trial. Patients may not be enrolled in any other interventional trial without permission of the Chief Investigator. Co-enrolment in observational studies is acceptable. All patients will only be enrolled once into the trial. The investigator will be responsible for checking the patient notes against the screening/enrolment log at site prior to screening to ensure that the patient is not already enrolled in the trial.

6.3.1.6 Screening procedures and pre-randomisation investigations

Written informed consent to enter and be randomised into the trial must be obtained from parents/guardians/person with legal responsibility (including legal authorities) for children, after explanation of the aims, methods, benefits and potential hazards of the trial and BEFORE any trial-

specific procedures are performed. The only procedures that may be performed in advance of written informed consent being obtained are those that would be performed on all patients in the same situation as a usual standard of care.

6.4 Interventions

Arm A: Experimental intervention: cross-linking in one or both eyes

Arm B: Control Intervention: standard management, provision of glasses

6.4.1 Arm A

6.4.1.1 Cross-linking

Cross-linking in one or both eyes (according to whether progression is confirmed in one eye or both eyes), under general or local anaesthesia as applicable, followed by standard management.

Following removal of corneal epithelium and administration of riboflavin drops, ultraviolet light will be administered according to standardised parameters of 10mW/cm^2 for a 5.4J/cm^2 total energy dose.

Like adults, children and young adults will experience some levels of stress and anxiety when undergoing medical treatment involving a surgical procedure. Special care, assistance and information will be provided to the children to alleviate their concerns. In bilateral cases in which there is randomisation to cross-linking the interval between procedures on the 1st and 2nd eye will be discussed with the patient and parents/guardians, and the preferred schedule will be decided on a case by case basis. To help patients for cross-linking feel more at ease during the procedure, they will be offered to choose between three different forms of anaesthesia: local anaesthesia with eye drops alone, drops with sedation and general anaesthesia. The 'Guidance on clinical research involving infants, children and young people: an update for researchers and research ethics committees' (2014) from the Royal College of Paediatrics and Child Health acknowledges that sedating active infants and children may be essential for some procedures which of themselves are of minimal risk. It states that sedation in healthy infants and children carries minimal additional risk and is usually associated with no more than occasional vomiting or short-lived disturbance of sleep. Only children who by themselves or their parents wish to do so will be sedated. General anaesthesia will only be performed in the youngest children, in whom the CXL procedure would not otherwise be feasible.

Sedation and general anaesthesia will be performed by experienced anaesthetic staff in the trial centre hospitals, who possess the necessary experiences, competencies, and skills to carry out the procedures and to deal immediately with any adverse effects. Participants will be monitored during and for approx. 2 hours after the procedure before being discharged home. One week following the CXL procedure, and subsequently as necessary, participants will have an eye examination to confirm corneal re-epithelialisation.

Riboflavin drops are procured as regular hospital stock following local site procedure. Sites should request and be able to provide a certificate of conformity or analysis for any batch of riboflavin used for the trial and this should be kept within the investigator site file. According to regulatory requirements set out by the MHRA, all drops that are used for the purpose of the trial need to be labelled as 'for local use only'.

6.4.2 Arm B

6.4.2.1 Standard management

Standard management alone, including refraction testing with provision of glasses and/or specialist contact lens fitting. Glasses or contact lenses to be provided for one or both eyes as required for best corrected visual acuity. Those patients who develop advanced disease and poor spectacle- and lens-corrected visual acuity during the course of the trial will be offered corneal transplantation.

6.4.3 Treatment schedule

Patients randomised to cross-linking will be added to a surgical list following enrolment and a letter will be sent to the patient with confirmation of the surgery date. Patients randomised to CXL will receive treatment no later than 4 weeks following randomisation but as soon as is feasible in all cases.

For participants with both eyes eligible, management of the second eye will be according to the randomised allocation for the first eye, unless there is a specific patient preference not to do so. The eye with the more advanced keratoconus at the time of randomisation will be categorised as the study eye for the primary analysis. Participants with both eyes eligible and who are randomised to CXL, can choose whether to have the procedure on both eyes at the same time. For participants with only one eye eligible at the time of randomisation, if during the course of the study the second eye has progressive keratoconus then management will be according to the randomised allocation.

Those participants with keratoconus progression identified on the basis of clinically significant worsening of vision during the study follow up will be offered further management on a patient-by-patient basis. Those participants who are randomised to CXL but choose not to have the surgery will be managed according to standard care.

6.4.4 Concomitant care

For patients on pre-existing treatment for allergic conjunctivitis, this will be continued as required for the treatment of the respective condition.

All concomitant medication taken by patients will be reviewed during enrolment and advice given as to whether this can be continued during the trial. It is likely that this will already be covered by the existing exclusion criteria.

6.4.5 Protocol treatment discontinuation

In consenting to the trial, participants are consenting to trial treatments, trial follow-up and data collection. As participation in the trial is entirely voluntary, the participant may choose to discontinue trial treatment at any time without penalty or loss of benefits to which they would otherwise be entitled. Although not obliged to give a reason for discontinuing their trial treatment, a reasonable effort should be made to establish this reason, whilst remaining fully respectful of the participant's rights.

Participants who discontinue protocol treatment, for any of the above reasons, should remain in the trial for the purpose of follow up and data analysis. They will be particularly encouraged to attend the 18 month follow-up visit.

6.5 Outcomes

6.5.1 Primary outcome

Primary outcome measure will be K_{\max}^* in the study eye at 18 months post-randomisation.

6.5.2 Secondary Outcomes

- a) Keratoconus progression (yes/no) defined as >1.5 dioptre increase in K_{\max}^* from baseline (at randomisation) to 18 months **or** requirement for change from spectacle to rigid contact lenses correction of vision, as the latter precludes reliable topography measures
- b) Time to keratoconus progression
- c) Uncorrected and best corrected visual acuity (measured as logMAR)
- d) Refraction (measured dioptres spherical equivalent, myopia and astigmatism)
- e) Apical corneal thickness measurement (ultrasound) **
- f) Quality of life as assessed by CHU9D and CVAQC questionnaires

* We will use K_{\max} measurements as the indicator of disease progression. The probability is high that K_{\max} increases >1.5 D would discriminate a true change in the steepest corneal meridian from artefact. A change of this magnitude is clinically significant, indicating a likelihood of improved visual acuity with correction of the refractive change; for example benefit from spectacle provision in an eye that previously had good unaided vision, a change in spectacle lens correction, or progression from spectacle wear to contact lens correction. K_{\max} will be measured 3 times by a masked observer at each visit during the trial and the mean value used in analyses.

** Apical corneal thickness measurement:

Biomechanical and ultrastructural studies to date have not been able to demonstrate the mechanisms by which CXL stiffens the cornea. The Keralink study will examine changes in thickness of the cornea by ultrasound as topography measurements do not provide accurate and reproducible thickness measurements. Cone apex thickness measurements will be correlated with changes in corneal shape and visual parameters. This will confirm whether arrest of keratoconus progression following CXL is accompanied by arrest in progressive thinning.

Keratoconus disease progression criteria:

- (i) At six months following randomisation and each subsequent follow up visit, corneal topography in each eye will be reviewed for possible progression, defined as a K_{\max} increase >1.5 D from baseline.
- (ii) Bearing in mind the inter- and intra-test variation in topography analysis, any patient found to have >1.5 D increase in K_{\max} will need to have this confirmed at a subsequent visit (i.e. 3 months later). Participants who have unconfirmed progression at the 18 month follow-up visit will need this confirmed at a further visit at 21 months.

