Study Type	This is a multicentre, UK based, randomised controlled trial comparing the efficacy and safety of cross linking surgery with standard clinical care in patients aged 10-16 years with progressive keratoconus.
Date of First Enrolment	June 2016
Target Sample Size	60
Primary Outcome(s)	
Primary outcome measure is K_{max} in the study eye at 18 months post randomisation
 
NB. The study eye is defined as the eye with the more advanced keratoconus at randomisation. The same intervention will be offered for the second eye for patients with progression in both eyes, unless the patient does not wish to receive the same intervention.

Key Secondary Outcomes	
(a) Keratoconus progression (yes/no) defined as >1.5D increase in K_{max} from baseline (randomisation) to 18 months or requirement for change from spectacle to rigid contact lens correction of vision
 
(b) Time to Keratoconus progression
 
(c) uncorrected and best corrected visual acuity (measured as logMAR)
 
(d) refraction (measured in dioptres of myopia and astigmatism)
 
(e) central corneal thickness (ultrasound)
 
(f) quality of life as assessed by CHU9D and CVAQC questionnaires

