6.10.4.2 Statistical Methods – Outcomes

For each patient the eye with the more advanced keratoconus at the time of randomisation will be defined as the study eye for the primary analysis. The analysis of the primary outcome will be performed using a linear mixed model fitted to all K_{\max} values recorded after randomisation. K_{\max} at randomisation, treatment group, follow-up time, the interaction between treatment and time, and the stratifying variables centre and whether each patient has only one eye eligible will be included as fixed effects and patient will be included as a random effect. This analysis is equivalent to modelling the change in K_{\max} adjusting for K_{\max} values at randomisation. Model assumptions will be assessed, and a logarithmic transformation used if this improves normality of the residuals. The impact of missing K_{\max} values due to the unreliability of topography measurements in patients who are unable to abstain from wearing lenses for 7 days pre-examination following rigid contact lens wear will be mitigated by applying appropriate multiple imputation methods to estimate these values.

Similar linear mixed models will be fitted for continuous outcomes such as uncorrected and best corrected visual acuity measured at randomisation and on more than one occasion during follow-up. Uncorrected and best corrected visual acuity will be measured in logMAR using an ETDRS chart at a distance of 4 metres.

In patients for whom both eyes show progression at the time of randomisation, information from both eyes will be included in a secondary analysis including eye as a fixed effect and patient as a random effect.

Cox survival analysis method will be used to estimate time to Keratoconus progression in each treatment group. Analysis will be stratified by the stratifying variables, centre and whether each patient has only one eye eligible, and patients who do not progress during the course of the trial will be censored at their last follow-up visit.

We will also explore how health and visual disability in children and young patients with keratoconus relate to changes in K_{\max} . CHU9D is a nine-question paediatric generic preference based measure of health outcome which provides a descriptive health profile as well as a utility score and has been validated for self-completion in an adolescent population (11-17 years)¹². CVAQC is a 25-item vision specific questionnaire designed for children¹³.

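### Section 6.5.2 counts a change to rigid lenses as progression in outcome (a) but leaves it out of the only visit-by-visit progression criteria, so time to progression (b) can score some lens switchers as event-free and censored

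*Protocol*

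**What the plan says.** Section 6.5.2 of the protocol describes progression in three places.

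- **Outcome (a)**, progression yes/no, has two components: a Kmax rise of more than 1.5 D from baseline to 18 months, or "requirement for change from spectacle to rigid contact lenses correction of vision, as the latter precludes reliable topography measures". The structured summary (1.3) lists the same alternative among the key secondary outcomes: "requirement for change from spectacle to rigid contact lens correction of vision".
- **Outcome (b)** reads in full "Time to keratoconus progression". It has no event definition of its own and no reference back to (a).
- **The block headed as disease progression criteria** says that from month 6 "corneal topography in each eye will be reviewed for possible progression, defined as a K_{\max} increase >1.5 D from baseline", and that "any patient found to have >1.5 D increase in K_{\max} will need to have this confirmed at a subsequent visit". A lens change is not mentioned. The footnote to the outcomes says "We will use K_{\max} measurements as the indicator of disease progression".

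Section 6.10.4.2 analyses (b) with a Cox model in which "patients who do not progress during the course of the trial will be censored at their last follow-up visit". It does not say which definition of progression decides who has progressed. Multiple imputation of Kmax values lost to rigid lens wear is described in the paragraph on the primary mixed model, not in the Cox paragraph.

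**The concern.** A time-to-event outcome needs a rule that assigns each event to a visit. Outcome (a) cannot supply one as written, because its Kmax part compares baseline with month 18 and its lens part carries no date. Criteria (i)-(ii) do work visit by visit, so an analyst programming (b) would naturally turn to them, and they have no lens component.

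The protocol itself gives the reason why this matters: the lens change is in (a) because rigid lenses stop topography from being reliable. A switcher without usable topography can neither meet nor confirm a Kmax criterion. Under (i)-(ii) that child would be carried as at risk through visits at which no event could be seen, then censored at the last visit attended, although (a) already counts the child as progressed.

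At stake is a named key secondary outcome. Outcomes (a) and (b) could disagree about who progressed, (b) would have fewer events, and the censoring would be related to worsening, since the protocol treats the lens change as a sign of it.

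**Working it through.** **1. Text comparison**

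| Place | Kmax rise >1.5 D | Change to rigid lenses | Dated by visit | Confirmation |
|---|---|---|---|---|
| 1.3 and 6.5.2, outcome (a) | yes, baseline to 18 months | yes | no | not stated |
| 6.5.2, criteria (i)-(ii) | yes, from month 6 | no | yes | next visit, on topography |
| 6.5.2, outcome (b) | not stated | not stated | not stated | not stated |
| 6.10.4.2, Cox analysis | not stated | not stated | censoring at last follow-up visit | not stated |

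The two definitions differ in their components, not only in timing, and nothing in (b) or in the Cox paragraph chooses between them.

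**2. Which children are affected**

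Section 6.10.4.2 ties lens-related missing Kmax to patients who cannot abstain from lenses for 7 days before the examination. A switcher who can abstain still has topography at the three-monthly visits in Table 1 and may be an event by Kmax. The children at risk of being lost from (b) are those who switch, cannot abstain, and had no confirmed Kmax rise before the switch.

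**3. Illustration of size**

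The protocol states no event count, hazard ratio, lens-switch rate or power for (b), so there is no figure to reproduce. The inputs below are assumptions, except for 30 per arm and 10% loss, which are in section 6.7.

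*Simulation.* 30 per arm; visits at 6, 9, 12, 15 and 18 months; constant hazard per visit; 10% random loss; two-component progression by 18 months of 40% in controls and 10% with CXL; log-rank test at two-sided 5%. A share of events, the same in both arms, is labelled as lens switches that Kmax does not detect.

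| Share of events lost | Power, about | Observed control progression, about |
|---|---|---|
| 0% | 78% | 38% |
| 10% | 71% | 35% |
| 20% | 65% | 31% |
| 30% | 58% | 27% |
| 50% | 42% | 19% |

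If 20% of events are lens switches but half of those children can abstain and are caught by Kmax, power is about 72%.

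*Cross-check by formula.* Power ≈ Φ(√(E/4) × |ln HR| − 1.96), with 27 evaluable per arm (30 less 10%).

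- HR = ln(0.9)/ln(0.6) = 0.21, so |ln HR| = 1.58.
- All events counted: E = 27 × (0.40 + 0.10) = 13.5; √3.375 × 1.58 − 1.96 = 0.94; power about 83%.
- 20% lost: E = 13.5 × 0.8 = 10.8; √2.7 × 1.58 − 1.96 = 0.63; power about 74%.
- 10% lost (a 20% share, half able to abstain): E = 12.2; power about 79%.
- 50% lost: E = 6.8; power about 54%.

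The formula gives higher power throughout, but the same direction and a loss of similar order. With a weaker assumed effect of 40% versus 20% (HR 0.44), it gives about 38% with all 16.2 events counted and 30% with a quarter of them lost, so (b) would have little power under either definition.

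**4. What the illustration does not show**

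The lens share is equal in both arms, so progression shrinks in proportion. At a 20% share the observed proportions are about 31% and 8%, still roughly 4 to 1. This measures lost events. It does not measure bias in the hazard ratio.

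**The case against.** The best answer is that (b) inherits (a). Outcome (a) defines the term, (b) reuses it on the next line, and the summary in 1.3 gives only the composite. Criteria (i)-(ii) can then be read as the confirmation rule for the Kmax route, since a lens change has no topographic test variation to confirm. This reading is reasonable, and it is why the point is that switchers *can* be censored, not that they will be. It does not remove the problem. The protocol never says it, the criteria carry a general heading, and even on this reading nothing dates a lens event or says whether it needs confirmation.

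A second answer is that event dating and censoring belong in the statistical analysis plan. That would hold for missing detail. Here one section states two component sets for the same word, and the analysis plan would have to override one of them.

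Two stronger readings are tempting, and the protocol supports neither. A reader might infer that every lens switcher loses any chance of an event in (b). That is wrong for those who can abstain for 7 days, and the footnote in 6.5.2 itself gives a move from spectacles to contact lenses as an example of what a Kmax change of this size can mean, so some switchers may already have met the Kmax rule. A reader might also infer that the treatment effect is biased, with the loss falling mainly on controls. That is plausible if CXL works, but the protocol has no data on it and the calculation above does not test it.

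**Conclusion.** The inconsistency stands as a matter of text. Progression has two components in (a) and one in the visit-level criteria, and (b) is tied to neither. Under the literal reading, switchers without usable topography are progressors in (a) and can be censored non-events in (b).

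Its size cannot be derived from the protocol. Under the assumed 40% versus 10%, a 20% share of undetected events costs about 13 percentage points of power by simulation (78% to 65%), or about 6 if half of switchers can abstain (78% to 72%). The outcome is secondary and has no stated power. The primary outcome, Kmax at 18 months, and the sample size in 6.7 do not depend on this definition. The point should be settled before the analysis is fixed, but it does not threaten the trial's main conclusion.

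**What to change.** In 6.5.2:

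- State that outcomes (a) and (b) use the same two components.
- State that the confirmation rule in (ii) applies to the Kmax route only.
- State that a lens-change event is dated at the visit where the requirement is recorded, using the same eye definition as the Kmax component. Criterion (i) refers to each eye, so the eye or eyes that count should be named once for both components.

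In 6.10.4.2, censor non-progressors at the last visit at which progression could be assessed, not simply the last one attended.

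The cost is a few sentences. Acuity with spectacles or contact lenses is already scheduled at every visit, but the requirement to change correction should be recorded explicitly. There is one small downside: under 6.9.2 site clinicians are not masked, so the lens decision may be made by someone who knows the allocation. A Kmax-only sensitivity analysis of (b) would show whether the result depends on that component.

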6.5.3 Compliance and adherence

Investigators and staff at site should follow local procedures for ensuring informed consent for CXL has been given, and that all patients have had sufficient opportunity to ask questions about the surgery.

Patients in CXL and standard care groups will be required to comply with the follow up schedule. All patients will be followed-up at 3, 6, 9, 12, 15 & 18 months from randomisation. However, if a participant first shows signs of progression at the 18 month follow-up visit, this would need to be confirmed at an additional 21 month visit. Site staff will be responsible for booking these

appointments and contacting any patients who do not attend to rearrange the appointment. No additional research visits will be required for patients needing surgery for their second eye.

6.6 Participant timeline

Table 1. Schedule of enrolment, interventions, and assessments.*

Study parameter	Consent, Screening, Randomisation	Treatment	Months post randomisation							
			3	6	9	12	15	18	21**	
Clinical examination and general eligibility assessment	x									
Informed consent and eligibility screening	x									
Corneal topography (Pentacam*)	x		x	x	x	x	x	x	x	
Visual acuity (unaided, spectacle- and contact lens-corrected as applicable)	x		x	x	x	x	x	x	x	
Refraction (measured dioptres myopia and astigmatism)	x		x	x	x	x	x	x	x	
Corneal thickness (ultrasound)	x		x	x	x	x	x	x	x	
Confirmation of eligibility	x									
Randomisation	x									
CXL Treatment		x ***								
CHU9D and CVAQC (QoL)	x		x		x			x		
Adverse Events	x	x	x	x	x	x	x	x	x	

All follow up visits will have a window of ± 28 days. CXL treatment should be undertaken within 4 weeks randomisation.

* Pentacam measurements prior to enrolment are used as the comparator for confirmation of keratoconus progression and thereby trial eligibility. For feasibility reasons, if patients referred for trial evaluation have had Pentacam topography in the community or in referring eye clinics, these measurements will be used to assess trial eligibility.

Pentacam measurements for confirmation of trial eligibility and for outcome assessment will be by standardised methodology. To improve repeatability, three measurements of each eye will be taken by a masked observer at each trial examination from randomization onwards and the mean used to determine progression.

The Pentacam K_{max} measurement which confirms eligibility prior to randomisation will be used as the baseline K_{max} for outcome assessment.

** Only participants with unconfirmed progression at the 18 month visit will have an additional 21 month visit to confirm progression.

*** All patients undergoing CXL treatment will have a non-research 1 week follow up appointment

as standard of care.

